9. RESEARCH DESIGN AND METHODS

This is a 6-week un-blinded, 2-arm randomized (1:1) controlled clinical pilot study. The overarching objective of this study is to determine the acceptability and feasibility of an acceptance and commitment therapy (ACT) intervention for the management of chronic pain adapted to aPLWH. To accomplish this objective this project will:

- 1) Train lay personnel to perform ACT to determine feasibility of this approach for future implementation,
- 2) Conduct audio recorded, uncontrolled group ACT in aPLWH to generate participant feedback and questionnaire data to inform ACT adaption with the assistance of a steering committee, and
- 3) Conduct an audio recorded, pilot randomized controlled trial (RCT) evaluating the acceptability of adapted ACT compared to pain education.

[figure not shown]
Due to concerns about COVID-19 the study procedures can be conducted remotely using Zoom teleconference services.

At completion of this project we expect to have successfully trained lay personnel to perform group ACT, adapted ACT from quantitative and qualitative data collected from an uncontrolled study of group ACT, and determined whether ACT is acceptable and feasible as an intervention in aPLWH. These expected outcomes may benefit other aging populations with chronic pain that are enriched for psychosocial co-morbidities such as persons who inject drugs, the socioeconomically disadvantaged, and racial or gender minorities. This proposal is aligned with the Office of AIDS Research High Priorities to better understand “HIV-associated comorbidities” which includes pain and to “Reduce Health Disparities in treatment outcomes of those living with HIV/AIDS” and with the National Pain Strategy to “expand investment … in the development of safe and effective pain treatments.”

Research Design and Procedures:

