If patients have had an antiretroviral resistance test during routine care, that data will be collected via chart abstraction.

Clinical Management Issues

This is a minimal risk study. No toxicities are anticipated a no treatment or invasive procedures are being performed as part of the study. However possible risks include:

Emotional distress

This behavioral intervention bring up past trauma or experiences that cause emotional distress. A highly experienced psychologist with post traumatic stress disorder experience is the Co-investigator of this study and will assist in triage as needed. In addition, the Owen Clinic has embedded psychiatrists that are available daily for emergency evaluations and will be utilized if any study personnel raise concerns about the state of participants. Emergency room evaluations will be encouraged if distress occurs after hours. Of note the AntiViral Research Center has a 24 hour physician on call to assist with triage of participants in various studies.

Selected Pain Interview

Participants will be asked to complete a short survey concerning their pain and pain treatment methods. These surveys will take place during the second (2nd) Arm 2 study visit.

Criteria for Discontinuation

- Subject requests to withdraw participation
- Primary care provider requests for subject withdrawal based on the provider's belief that study participation is no longer in subject's best interest
- Medical provider belief that the patient has life threatening clinical condition
- By the discretion of the site IRB, NIH or investigator

Statistical Considerations

This section briefly describes the planned statistical analysis. The statistical Analysis Plan (SAP) provides details. If the language in this section differs from the language in the SAP, the SAP takes precedence.

Analytic Plan: [name] and her team will lead all statistical analyses for this study. For the RCT we will obtain descriptive statistics to compare baseline characteristics between study arms (ACT versus pain education). Categorical variables will be analyzed using Fisher's Exact Test and continuous variables using Wilcoxon Rank Sum Test. To determine acceptability of group ACT, we will use the CSQ at endpoint of the intervention as the primary outcome. This is a pilot study, but we will utilize a superiority

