study design, and incorporate an intent-to-treat (ITT) approach to analyze the outcome data. We will employ multivariable logistic regression analysis to study the association between clinical (duration of HIV infection, nadir CD4, BPI), demographic (i.e., age, sex, duration of HIV infection, nadir CD4), and psychosocial factors (i.e., substance use, loneliness) and intervention arm adjusting for baseline demographic and clinical characteristics. Variables significantly associated with treatment groups and outcome ($p < 0.10$) including appropriate interaction terms, will be included in the final multivariable logistic regression model as covariates. CSQ at midpoint and proportion of sessions attended will be evaluated in sensitivity analyses. The study procedures can occur in person or remotely. We will statistically evaluate this process and compare group cohesion scores between persons who attend live (if feasible) and remotely.

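### Screening covariates on association with both randomised arm and outcome (p<0.10) leaves the final model to chance imbalance; naming one or two prognostic covariates in advance is better

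*Combined protocol and SAP*

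**What the plan says.** Section 9 describes the trial thus: "This is a 6-week un-blinded, 2-arm randomized (1:1) controlled clinical pilot study". Under Statistical Considerations, the Analytic Plan makes endpoint CSQ the primary outcome, with a superiority, intention-to-treat approach.

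Three statements bear on covariates:

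- For the randomised trial, "we will obtain descriptive statistics to compare baseline characteristics between study arms". Fisher's exact and Wilcoxon rank sum tests are named for this.
- A multivariable logistic regression will examine clinical, demographic and psychosocial factors. Seven distinct ones are named: duration of HIV infection, nadir CD4, Brief Pain Inventory (BPI), age, sex, substance use and loneliness. The sentence mentions adjustment for baseline characteristics but fixes no set.
- Entry to the final model is then decided by the data. The rule picks out "Variables significantly associated with treatment groups and outcome", with a threshold of p<0.10. It says that these, together with interaction terms that it does not name, "will be included in the final multivariable logistic regression model as covariates".

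The same section says that a separate SAP gives the details and takes precedence. No separate SAP text is in the document supplied.

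**The concern.** Requiring association with treatment group is a way of looking for confounders in observational data. Under randomisation, a baseline difference between arms carries no information about which variables deserve adjustment. What makes a covariate useful here is that it predicts the outcome, because adjustment then removes residual variance.

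Requiring both associations means that a good predictor of CSQ enters only when it also happens to be imbalanced. The set of adjusters, and so the reported arm effect, then depends on the luck of the allocation. The precision that the baseline data could give is mostly not used. The trial is small, and the plan still frames its primary comparison as one of superiority.

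**Working it through.** **Inputs from the document.** Allocation is 1:1. The rule is p<0.10 on arm and on outcome. There are seven named candidates. The Aim 3 text randomises 40 (20 per arm), while Step 2, Entry Evaluations and Randomization, says 20 (10 per arm), so both sizes are shown.

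**Inputs assumed, because none are given.** Two-sided alpha of 0.05; a true effect of 0.8 SD; independent candidates; two of the seven prognostic, each with correlation r with the outcome; independent participants.

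**The plan's own figure.** No power statement exists to reproduce. The only sample-size arithmetic is the allowance for about 15% loss: 40/(1 − 0.15) = 47.1, or 48 for equal arms, close to the stated target of 50.

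**Step 1: how often the rule keeps a prognostic variable.** Under randomisation, P(arm screen passed) = 0.10 however prognostic the variable is. Since P(both passed) ≤ P(arm screen passed), inclusion cannot exceed about 10%. Simulated inclusion at 20 per arm was 3 to 8% across r = 0.1 to 0.4. With a single covariate at r = 0.5 it was 8.6%, against 93% had the screen been on outcome alone. Meanwhile the chance that at least one of seven candidates looks imbalanced is 1 − 0.9^7 = 0.52.

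**Step 2: what could be gained, approximately.** With two independent covariates the residual variance is 1 − 2r², so the effective standardised effect is 0.8/√(1 − 2r²), and power ≈ Φ(effect × √(n/2) − 1.96). At n = 20, √(n/2) = 3.162.

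- Unadjusted: Φ(0.8 × 3.162 − 1.96) = Φ(0.57) = 0.72. Simulation gave 0.69 to 0.71.
- r = 0.2: 0.8/√0.92 = 0.834; Φ(0.68) = 0.75.
- r = 0.4: 0.8/√0.68 = 0.970; Φ(1.11) = 0.87.

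This ignores lost degrees of freedom, so it slightly overstates power.

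**Step 3: simulated power, linear model, 20 per arm.** Ranges are over repeated runs, with Monte Carlo error of up to about 1 point. Gains are approximate and can differ by a point from the rounded columns.

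| r (each of two) | Plan's rule | Right two pre-specified | Gain |
|---|---|---|---|
| 0.1 | 67% | 68% | about 1 |
| 0.2 | 67–68% | 70–71% | about 4 |
| 0.3 | 66–67% | 75–76% | about 9 |
| 0.4 | 67–68% | 82–83% | about 15 |

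Unadjusted power in the r = 0.4 setting was 69 to 70%. If the two covariates named in advance are not prognostic, power there is 67%, the same as the rule and 2 to 3 points below no adjustment.

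At 10 per arm with r = 0.4: rule 35 to 36%, unadjusted 40%, pre-specified 49%.

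**Step 4: type I error.** At r = 0.4 and 20 per arm it was 3.6 to 4.0% under the rule and 4.8 to 5.2% with pre-specified covariates. With one prognostic covariate the rule gave 3.4 to 4.4%. The lowest value seen was 2.4%, with two covariates at r = 0.5. All departures are on the conservative side.

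**Step 5: logistic version.** The plan names logistic regression but gives no CSQ cut-off. With a dichotomised score, one prognostic covariate and 20 per arm, power for rule against pre-specified was 0.47 vs 0.55 (r = 0.3), 0.50 vs 0.63 (r = 0.5) and 0.48 vs 0.66 (r = 0.6). The direction is the same, but part of the gain is test size: type I error was about 0.055 pre-specified and 0.031 to 0.039 under the rule. Forcing all seven covariates into the logistic model gave type I error of about 0.08 to 0.10 at 20 per arm and 0.18 to 0.21 at 10 per arm.

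**The case against.** - **The size depends on assumed correlations.** This stands. Nothing in the document says that any baseline variable predicts satisfaction. A reader might infer a flat 15-point loss of power, but that needs two covariates at r = 0.4 and the right two chosen out of seven. At weak correlations the gain is 1 to 4 points.
- **Most of the difference is a gain not taken.** This also stands. Against no adjustment, the rule costs only 1 to 3 points at 20 per arm.
- **A reader might infer that the test is invalid.** The calculations do not support this, because the error rate falls below nominal.
- **The final model may not be the primary comparison.** The text does not name that model's dependent variable, and its preceding sentence relates factors to intervention arm. The ambiguity is real. However, no other covariate set is given for comparing CSQ between arms.
- **The word joining arm and outcome could mean either.** The text does not say so. An either/or rule would give 77 to 78% power at r = 0.4 and 20 per arm, and 39% at 10 per arm. That is still below pre-specification, and the model is still chosen from the data.
- **Interactions.** A reader might infer that added interaction terms must change what the arm effect means. That depends on which terms enter and how covariates are coded, and it was not simulated. Section 10 also gives a reason to look at sex as a modifier. What remains is that the terms are not named.
- **The SAP governs, and this is a pilot.** A separate SAP may already fix the covariates. The pilot's focus on acceptability lowers the stakes, but the superiority framing keeps precision relevant.

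**Conclusion.** The concern holds in a limited form. On its plain reading the rule excludes a prognostic variable in about 90% or more of trials and lets chance imbalance choose the model. That follows from randomisation alone and needs no assumed effect size.

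The cost in power does rest on assumptions. Relative to naming the right two covariates, it runs from about 1 point at r = 0.1 to about 15 at r = 0.4 (20 per arm, 0.8 SD, continuous score). It is zero if the covariates named are not prognostic. These figures treat participants as independent, although both arms are delivered in groups of 8 to 10.

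The case is one of better use of baseline data and a fixed model, not of an inflated error rate. Whether CSQ should be analysed by linear or logistic regression is a separate question, which this point does not settle.

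**What to change.** Delete the p<0.10 screen on treatment group and outcome. In its place, name one or two baseline covariates that are already collected and expected to predict CSQ. Treatment expectations and BPI interference, both measured at week 0 according to the Assessments text, are examples. Suitable wording would be: the primary comparison of endpoint CSQ between arms will adjust for baseline treatment expectations and baseline BPI interference, whatever their balance between arms.

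Do not force in all seven candidates. Do not use baseline significance tests to choose covariates. Report interaction or moderator analyses, for example by sex, separately as exploratory. If a separate SAP already fixes the covariates, bring this section into line with it.

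The cost is wording only. There are two downsides. Chance imbalances in unlisted variables would be described but not adjusted for, and poorly chosen covariates would cost about 2 to 3 points of power against no adjustment at 20 per arm.

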For AIM 3 Acceptability and Feasibility of Adapted ACT Intervention: Forty persons will be randomized to either group adapted ACT or group education. In anticipation of ~15% early discontinuation or lost to follow up, we plan to recruit 50 participants overall. All sessions will be audio recorded for future analysis. Adapted ACT will be provided by ACT therapists in weekly 2-hour group (8-10 persons per group) sessions for the 6 weeks of the intervention and will include brief review of at-home practice assignments, introduction of new material and end with assigned at-home practice exercises. Participants randomized to control will also participate in 2-hour 6 weeks group sessions (8-10 persons) using the “Take Charge of Your Pain” handbook developed by Investigators at the Weill-Cornell Translational Research Institute for Pain in Later Life (Table 2). All sessions will be audio recorded for future analysis. Study participants will complete assessments at baseline, week 3 (midpoint) and week 6 (endpoint). Following completion of study we will assess for persistence of ACT activities and practices by a short telephone follow up. Participants may come to the AVRC for an in person discussion but this will not receive monetary compensation.

Remote Engagement of Study Participants

To ensure safety of participants (who are all older adults with the co-morbidity of HIV) during COVID-19 and respect the “shelter at home” state-wide order this aim will be performed 100% virtually. The protocol specifically has been adapted to include

- 1) over the phone consent. This is a minimal risk study and with COVID-19 the risk of an in-person evaluation greatly outweighs the potential benefit.
- 2) Questionnaires to be completed via a) online through REDCAP mechanism that provides a link and password to allow participants to securely complete questionnaires or b) complete paper questionnaire mailed to participant with stamped envelope for return with only the study ID on papers to protect participant privacy
- 3) Online group meetings using Zoom with password to prevent hackers.
- 4) Compensation provided either using an electronic gift card or a script mailed to the study participant.

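### The final model admits a baseline covariate only if it is associated at p<0.10 with the randomised arm as well as the outcome, so a prognostic covariate is dropped about nine times in ten

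*Combined protocol and SAP*

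**What the plan says.** All of this is in section 9, Statistical Considerations, Analytic Plan, unless another place is named.

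- **Baseline comparison.** For the randomised trial, "we will obtain descriptive statistics to compare baseline characteristics between study arms". The tests follow: "Categorical variables will be analyzed using Fisher's Exact Test and continuous variables using Wilcoxon Rank Sum Test".
- **Primary outcome.** The CSQ score at the end of the intervention, analysed by intention to treat under a superiority design. The regression named is logistic, and no CSQ cut-point is given.
- **Candidate variables.** Duration of HIV infection, nadir CD4, BPI, age, sex, and "psychosocial factors (i.e., substance use, loneliness) and intervention arm". The same sentence ends with "adjusting for baseline demographic and clinical characteristics".
- **Entry rule.** "Variables significantly associated with treatment groups and outcome", at p<0.10 and with suitable interaction terms, "will be included in the final multivariable logistic regression model as covariates".
- **Sample size.** Section 9, For AIM 3: "Forty persons will be randomized to either group adapted ACT or group education", with 50 recruited to allow for about 15% loss. Section 9, Step 2, Entry Evaluations and Randomization, instead gives 20 in total, 10 per arm. Allocation is 1:1 throughout.
- **Precedence.** The section calls itself a brief description and defers to a statistical analysis plan. No separate plan was among the documents supplied.

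**The concern.** A covariate earns its place in a randomised comparison by predicting the outcome. Whether it happens to differ between the arms at p<0.10 says nothing about that. Because allocation is random, the hypothesis of no association between arm and a baseline variable is true by design. A test of it at 0.10 passes roughly one continuous variable in ten, strong and weak predictors alike. Requiring that test to be passed discards most of the variables that could sharpen the comparison of ACT with education. It also leaves moderate chance imbalances in prognostic variables uncorrected.

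A second problem is independent of the first. The rule needs the outcome data before the covariates are known, so the final model cannot be written down in advance.

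This point concerns main-effect covariates and does not address the interaction terms.

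**Working it through.** **Inputs from the documents.** Entry threshold p<0.10 (sidedness not stated; two-sided assumed); Wilcoxon for continuous and Fisher for categorical variables, taken to be the tests behind the screen; 1:1 allocation; 20 per arm (Aim 3 text) or 10 per arm (Step 2 text). The documents state no power, effect size or SD to reproduce. The one related figure is the recruitment target: 40/(1 − 0.15) = 47.1, or 48 with equal arms, close to the planned 50. If all 50 were randomised there would be 25 per arm, so that case is shown too.

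**Step 1: what size of imbalance is adjusted.** For an observed difference of d SD, t = d/√(2/n) on 2n − 2 degrees of freedom. The smallest difference that enters is t(0.95, 2n − 2) × √(2/n).

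| Per arm | t at 0.5 SD | p | Entry needs |
|---|---|---|---|
| 20 | 0.5/0.316 = 1.58 | 0.122 | 1.686 × 0.316 = 0.53 SD |
| 10 | 0.5/0.447 = 1.12 | 0.28 | 1.734 × 0.447 = 0.78 SD |
| 25 | 0.5/0.283 = 1.77 | 0.084 | 1.677 × 0.283 = 0.47 SD |

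These use a t-test. With the planned Wilcoxon test individual data sets scatter around the limit: at 20 per arm, observed imbalances of 0.45 to 0.55 SD were flagged in only 27 to 32% of simulated trials.

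**Step 2: how often a covariate is kept** (20,000 simulated randomised trials per setting, no treatment effect, assumed covariate–outcome correlation r of 0.3 to 0.7).

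- Arm test alone, Wilcoxon, 20 per arm: passed in 9.2 to 9.7% of trials, so dropped in about 90 to 91%.
- Both tests required, continuous outcome: kept in 5.8% (r=0.3), 8.8% (r=0.5) and 9.3% (r=0.7).
- Both tests required, outcome split at the median: kept in 4.2%, 7.8% and 9.3%.
- Binary covariates by Fisher's test, full enumeration at prevalences of 20 to 75%: the arm test passes 4 to 5%, so about 95% are dropped.
- At 10 per arm, a continuous covariate is dropped in about 91 to 98% of trials.

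At 25 per arm an imbalance of 0.5 SD would be flagged, but the drop rate stays near 90%, because it is set by the 0.10 level and not by the sample size.

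**Step 3: what it costs.** Assumptions, none from the documents: CSQ analysed as a continuous score in a linear model, true effect 0.8 SD, 20 per arm, one covariate. Power from simulation:

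| r | With the screen | Covariate fixed in advance |
|---|---|---|
| 0.1 | 69% | 68% |
| 0.2 | 70% | 71% |
| 0.3 | 70% | 72% |
| 0.4 | 68% | 75% |
| 0.5 | 72% | 81% |
| 0.6 | 72% | 86% |

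Differences of a point or two are within simulation error. At r=0.5 the null SD of the estimated effect is 0.303 with the screen and 0.279 with fixed adjustment. The variance ratio is (0.303/0.279)² = 1.18, so the screen costs about 18% in variance. Overall type I error with the screen is 4 to 5%.

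**The case against.** **The wording can be read otherwise.** If *and* was meant as association with either arm or outcome, a covariate with r=0.5 would be kept about 96% of the time at 20 per arm, and power would match fixed adjustment. The conjunctive reading is the literal one, and selection would be data-driven under both, so the sentence needs rewriting either way.

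**Baseline adjustment is mentioned.** It is, in the sentence before the rule, but that sentence names no set that stays in the final model. As written it relates baseline factors to intervention arm, which leaves even the dependent variable unclear.

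**The separate analysis plan may settle this.** It may, and it takes precedence. It could not be checked.

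**The power loss depends on favourable inputs.** This stands. The outcome is a satisfaction score, and nothing in the documents says how strongly BPI, age or loneliness predicts it. With three fixed covariates of which only one is prognostic, at r=0.2, power is 69% screened and 68% fixed, so nothing is gained.

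**The planned model is logistic.** This also stands. In logistic simulations the gain turns on the unstated cut-point: 43% versus 59% with a median split, r=0.5 and one covariate, but 48% versus 51% by likelihood ratio when 25% of participants exceed the cut and three covariates are fixed. In that last setting the Wald test does worse with adjustment (38%) than without (46%). At 10 per arm with three covariates, likelihood-ratio type I error is about 10%.

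**Stronger readings the documents do not support.** A reader might infer that the plan treats a non-significant baseline test as proof that the arms are equal. It offers the comparison as descriptive and draws no such inference. A reader might also quote the screen's chance of missing a true baseline difference, but under randomisation no true difference exists to be missed. Finally, a reader might infer that the screen invalidates the test. Error of 5 to 9% was seen only within the 17 to 19% of null trials left with an unadjusted imbalance above 0.35 SD; across all trials it is not inflated.

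**Conclusion.** The point holds for the rule as literally written. Association with the randomised arm is a precondition for adjustment, so at 20 per arm a continuous baseline covariate is dropped at least about 90% of the time whatever its prognostic value, and an observed 0.5-SD imbalance goes unadjusted. The drop rate needs only valid randomisation and the 0.10 level. The 0.5-SD statement needs 20 per arm or fewer.

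The consequence is lost precision and a model that is not pre-specified; the test remains valid. The size of the precision loss is uncertain: negligible if the best available covariate correlates 0.2 or less with endpoint CSQ, and 9 to 14 points of power at 0.5 to 0.6 under the linear model and assumed 0.8-SD effect. For a pilot with acceptability as its primary outcome and no stated power target, this is a worthwhile, inexpensive correction.

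**What to change.** In the Analytic Plan, and in the separate analysis plan if it carries the same rule:

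1. Delete the requirement that a covariate be associated with treatment group and outcome.
2. Name in advance one or two baseline covariates, already collected and expected to predict endpoint CSQ, and include them in the between-arm CSQ model whatever their baseline p-values.
3. State that model with the list: CSQ as a continuous score or, if logistic, the cut-point.
4. Report baseline characteristics descriptively by arm, and do not use between-arm p-values to choose covariates.
5. Reconcile the 40 and the 20 to be randomised, since this limits how many covariates the model can carry. With either number a logistic model supports few.

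The cost is wording only, with no new data. The downside is a small loss of precision if a named covariate turns out to be weakly prognostic, which is the reason to keep the list very short.
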